### 2.3 Eligibility criteria

All mainstream secondary schools in the ACT, both government and non-government, will be invited to participate in the evaluation of YAM. YAM is a suicide prevention and mental health promotion program designed for young people aged 14 – 16 years. All Year 9 students receiving the YAM program will also be invited to participate in the YAM evaluation. No exclusion criteria will be applied. However, schools in which there has been a recent suicide death, crisis or other occurrences which may make students vulnerable (e.g., a non-suicide death) will not participate in the evaluation study. The research team will work with the Suicide prevention Officer co-located within ACT Health and the Education Directorate of ACT to identify such schools.

### 2.4 Intervention

The YAM intervention is a structured program of lectures and interactive role play sessions, consisting of five 1-hour sessions presented over a 3- to 6-week period. More specifically, it consists of one x 1-hour interactive lecture about mental health at the beginning (session 1), three x 1-hour sessions of role-play (sessions 2, 3, 4), and one closing session (session 5). Participants are also provided with a 32-page booklet that reiterates much of the content and includes a localised list of well-being and help-seeking resources. Six educational posters are also displayed in each participating classroom for the duration of the intervention. Content topics are: (1) Awareness about mental health; (2) Self-help advice; (3) Stress and crisis; (4) Depression and suicidal thoughts; (5) Helping a troubled friend; and (6) Getting advice: who to contact.

Nominated YAM instructors attend a 4.5 day training session conducted by YAM certified trainers to be able to deliver the YAM intervention in schools. Participants in the training sessions will take part in role-play sessions to practice how to deliver the intervention, and they will receive feedback from trainers. Upon completion of the course, participants will become certified YAM instructors, and are able to deliver the five session YAM program to adolescents in Australia. YAM instructors can be anyone who has contact with youth, such as psychology and psychiatry professionals, social workers, youth counsellors, social assistants, school guidance counsellors, teachers, school nurses, youth advocates, or support group workers. It is recommended that YAM instructors should not be teachers in the schools in which YAM is being implemented.

### 2.5 Outcomes

*Primary outcome measure:* The primary outcome measure will be suicidal ideation severity, measured by Paykel's Suicidal Feelings in the General Population Questionnaire (PSFGPQ).

*Secondary outcome measures for mental health:* suicidal behaviour (attempt and self-harm); help-seeking intentions for suicide (General Help-Seeking Questionnaire, GHQ adapted); help-seeking behaviours for suicide (Actual Help-Seeking Questionnaire, AHQ adapted); depression (Patient Health Questionnaire Depression Scale, PHQ-8); suicide literacy (Literacy of Suicide Scale, LOSS short-form); stigma of suicide (Stigma of Suicide Scale, SOSS short-form), loneliness (UCLA 3 Item Loneliness Scale); confidence supporting peers, and mental wellbeing (Short Warwick-Edinburgh Mental Wellbeing Scale, WEMWBS short-form).

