## 1.2 Objectives

The primary aim of the YAM study is to determine whether there is a significant decrease in suicidal ideation severity across time (from immediate post-intervention and 3-month follow-up, compared to baseline) compared to a waitlist control group.

The study also aims to determine whether students receiving YAM compared to students receiving classes as usual (the waitlist control group), will have reported:

- a) Reduction in the rate of self-harm at 3-month follow-up;
- b) Increase in help-seeking intentions for suicide immediately post-intervention and 3-month follow-up;
- c) Increase in help-seeking behaviour for suicide immediately post-intervention and 3-month follow-up;
- d) Decrease in suicide stigma immediately post-intervention and 3-month follow-up;
- e) Increase in suicide literacy immediately post-intervention and 3-month follow-up;
- f) Decrease in depression symptoms immediately post-intervention and 3-month follow-up;
- g) Decrease in loneliness immediately post-intervention and 3-month follow-up;
- h) Increase in confidence supporting peers immediately post-intervention and 3-month follow-up;
- i) Increase in mental wellbeing immediately post-intervention and 3-month follow-up.

Process outcomes for the implementation of the YAM intervention in the ACT will also be evaluated; including:

- a) Number of schools contacted and signed on for participation in the YAM program;
- b) Number of Instructors and Helpers trained to deliver YAM;
- c) Number of schools that completed the YAM program;
- d) The extent to which the program was delivered as prescribed;

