### 1.3 Hypotheses

Immediately post-intervention and at 3-month follow-up, relative to baseline, it is hypothesised that student participants that have received the YAM intervention will report:

1. decreased suicidal ideation severity compared to control
2. greater reduction in rates rate of self-harm compared to control
3. greater increase in help-seeking intentions for suicide compared to control
4. greater increase in help-seeking behaviour compared to control
5. greater reduction in stigma relating to suicide compared to control
6. greater increase in knowledge relating to suicide compared to control
7. greater reduction in depression symptom severity compared to control
8. greater reduction in loneliness compared to control
9. greater increase in confidence supporting peers compared to control
10. greater increase in mental wellbeing compared to control

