#### **Actual Help-Seeking Questionnaire (modified) (Q9-10)**

The AHSQ assesses recent actual help-seeking behaviour in which the respondent either does or does not report having sought help from for a mental health problem in the past 3 months. In addition to the AHSQ, actual help-seeking from adults is measured by four items (yes/no) that assess the experience of help-seeking from adults, conditional on responses to the AHSQ. If students indicate that they have sought help from at least one adult for a mental health problem on the AHSQ, then four questions will be presented asking whether any of the adults that they have had contact with have made them feel supported, helped them get

through the situation, made the situation worse, or made them more likely to seek further help from adults. These items were drawn from the previous US Sources of Strength trial

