**General Help-Seeking Questionnaire (modified) (Q11)**

The GHSQ assesses intentions to seek help for personal or emotional problems from 11 different formal and informal sources (e.g. friend, parent, psychologist, or teacher). Respondents indicate how likely they are to seek help from each of the sources on a scale ranging from 1 (extremely unlikely) to 7 (extremely likely).

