#### **4.3 Students identified to be at immediate risk of suicide or other harm**

Student surveys will be confidentially viewed within 24 hours of completion by the research team as part of the monitoring and referral process to identify 'at-risk' respondents. Students who endorse any of the suicidal ideation or self-harm questions will be 'flagged' (specific criteria below) and the school Principal will be notified to coordinate follow up with these students by the school's wellbeing team in accordance with usual school procedures. The selection of these items has been made in consultation with the ACT YAM working group, ACT health and ACT Education Directorate. The research team will prepare the school Principal of this process ahead of time. Students will be notified of this referral process prior to them completing the questionnaire.

There are nine items for students will be flagged. A student will be flagged if they select the any of the following responses for:

- i) Have you felt, during the past 2 weeks, that life is not worth living? (sometimes or above)
- ii) Have you wished, during the past 2 weeks, that you were dead? For instance, that you could go to sleep and not wake up? (sometimes or above)
- iii) During the past 2 weeks, have you thought of taking your life, even if you would not really do it? (sometimes or above)
- iv) During the past 2 weeks, have you reached the point where you seriously considered taking your life or perhaps made plans how you would go about doing it? (rarely or above)
- v) Have you ever tried to take your own life? (yes)
- vi) When did you try to take your own life? (yes to any time selected)
- vii) Have you injured yourself on purpose in the past month? (yes)
- viii) Did you intend to experience pain or suffering as a result of your self-injury? (yes)
- ix) Did you intend to die as a result of your self-injury? (yes)

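### The help-seeking outcomes are labelled as being for suicide while the instruments are described as broader, and a 3-month recall at the immediate-post survey looks back mostly before the programme

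*Protocol*

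**What the plan says.** **Outcome labels.** Objective c in Protocol 1.2 reads "Increase in help-seeking behaviour for suicide immediately post-intervention and 3-month follow-up", and objective b attaches the same suicide qualifier to intentions. Section 2.5 repeats it for both outcomes: "help-seeking intentions for suicide (General Help-Seeking Questionnaire, GHQ adapted") and "help-seeking behaviours for suicide (Actual Help-Seeking Questionnaire, AHQ adapted"). In section 1.3, hypothesis 3 (intentions) keeps the qualifier, but hypothesis 4 reads only "greater increase in help-seeking behaviour compared to control".

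**Instruments.** Section 3.1 says that the modified Actual Help-Seeking Questionnaire (AHSQ, Q9-10) records whether the respondent does or "does not report having sought help from for a mental health problem in the past 3 months". It says that the modified General Help-Seeking Questionnaire (GHSQ, Q11) "assesses intentions to seek help for personal or emotional problems from 11 different formal and informal sources". Suicide appears in neither description.

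**Timing.** Section 2.6 has students fill in the same questionnaire at all three occasions: immediately before the programme, immediately after it, and at 3 months. Section 2.4 gives the programme as five sessions over 3 to 6 weeks. Objective c and the opening of 1.3 both call for a comparison of help-seeking behaviour at the immediate-post survey.

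**The concern.** Two separate problems affect these secondary outcomes.

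The first is the construct. Seeking help for suicidal thoughts and seeking help for any mental health problem are different behaviours, with different base rates and different groups of students to whom they apply. If the items are as 3.1 describes them, a result reported under the label in 1.2 and 2.5 would claim something the data do not show. If the items do carry a suicide stem, 3.1 misdescribes the instruments. One set of passages has to change.

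The second is the recall window, and it concerns behaviour only. A 3-month look-back asked a few weeks after baseline mostly covers time before any student had received the programme. A real increase in help-seeking could then appear small or absent at the immediate-post survey, and the null result could be misread as evidence that the programme did not change behaviour.

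**Working it through.** **Construct: the passages side by side**

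| Protocol section | Behaviour (AHSQ) | Intentions (GHSQ) |
|---|---|---|
| 1.2 Objectives | for suicide (c) | for suicide (b) |
| 1.3 Hypotheses | no qualifier (4) | for suicide (3) |
| 2.5 Outcomes | for suicide | for suicide |
| 3.1 Instruments | mental health problem, 3 months | personal or emotional problems |

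Section 3.1 disagrees with 1.2 and 2.5 for both outcomes, and 1.3 sides with neither throughout. The word adapted in 2.5 does not settle the matter, because the 3.1 entries are headed as modified versions and still describe the broader content.

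**Recall: inputs**

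- Recall period R: 3 months (3.1), taken as 13 weeks, with 12 weeks as a check.
- Gap g from baseline to the immediate-post survey: 3 to 6 weeks. This assumes the gap equals programme length (2.4), which the word immediately in 2.6 supports. Table 1 in 1.4 says only that both surveys fall in Term 2.
- The protocol gives no rate, effect size or power figure for help-seeking, so there is no planned figure to reproduce.

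**Share of the window before baseline = (R − g)/R**

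| g (weeks) | R = 13 | R = 12 |
|---|---|---|
| 3 | 10/13 = 77% | 9/12 = 75% |
| 4 | 9/13 = 69% | 8/12 = 67% |
| 5 | 8/13 = 62% | 7/12 = 58% |
| 6 | 7/13 = 54% | 6/12 = 50% |
| 8 | 5/13 = 38% | 4/12 = 33% |

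With R = 13 the share falls below half only when the gap exceeds 6.5 weeks.

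**What this does to the contrast (illustration, assumed rates).** Take a constant weekly rate λ, with the programme multiplying it by a rate ratio k from baseline onwards.

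- Control: P = 1 − exp(−λR). Assuming P = 20%, λR = −ln(0.80) = 0.2231.
- A window lying wholly after baseline, with k = 2: 1 − exp(−2 × 0.2231) = 36%, a difference of 16 points.
- Immediate-post: P = 1 − exp(−λ[(R − g) + kg]).
  - g = 3: 1 − exp(−0.2231 × 16/13) = 24.0%, a difference of 4.0 points, or 25% of the full difference.
  - g = 6: 1 − exp(−0.2231 × 19/13) = 27.8%, a difference of 7.8 points, or 49%.

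Over assumed control rates of 10% to 30% and rate ratios of 1.5 to 2, about 24% to 26% of the full difference is retained at g = 3 and about 47% to 51% at g = 6.

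With the 119 students per cluster arm in 2.7, the 20% example amounts to 119 × 0.040 ≈ 5 extra students at g = 3, or 119 × 0.078 ≈ 9 at g = 6. A fully post-baseline window would give 119 × 0.16 ≈ 19. This ignores clustering and dropout.

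**The 3-month survey.** If it falls about three months after the programme, the same recall period covers roughly the interval since the programme ended, and the pre-baseline share is about zero.

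**The case against.** **The items may be right and the description wrong.** Both instruments are called adapted or modified, and the survey in Appendix A is not reproduced. Section 3.1 may simply carry over the description of the parent scales. This stands. A reader might infer that help-seeking for suicide is not measured at all, and the document does not support that. It shows a contradiction, not which side is correct.

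**The label may be a slip of little consequence.** The executive summary speaks of increasing help-seeking without any suicide qualifier, and hypothesis 4 does the same, so a general instrument fits the overall goal. This is fair as to weight: these are secondary outcomes and the primary outcome is untouched. It does not remove the need to make the objectives, hypotheses, outcomes and instruments agree.

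**The overlap is the same in both arms and affects one survey.** Both parts of this are correct. The effect is attenuation, not bias towards either arm, and objective c is adequately measured at its second time point. The size also rests on the survey gap equalling programme length.

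**A stronger reading is tempting.** Section 4.3 says that for flagged students "the school Principal will be notified to coordinate follow up with these students". A reader might infer that these contacts inflate later AHSQ answers in both arms. The document does not support this as a finding. The instrument is described as asking about help sought, which school-initiated contact is not. The further items about contact with adults appear only after a student reports having sought help from an adult. No flag rate is given, so no size can be computed. Flagging runs in both arms on simultaneous surveys, so no bias towards one arm follows.

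**Conclusion.** The point holds in two limited parts.

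1. The protocol contradicts itself on what the help-seeking outcomes measure. This needs no assumption and is visible from 1.2, 1.3, 2.5 and 3.1. Which passages are wrong depends on the wording of Q9-11, which is not shown.
2. The immediate-post contrast for help-seeking behaviour is diluted towards zero in a non-differential way. About 54% to 77% of a 13-week recall window precedes baseline (50% to 75% with 12 weeks), provided the gap between surveys is 3 to 6 weeks. The estimate that roughly a quarter to a half of the effect is retained also rests on assumed rates and a constant-rate model, so it illustrates the problem and does not forecast the result.

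The recall point does not extend to the 3-month survey, nor to intentions, for which no recall period is described. Confidence is high that the passages conflict and moderate on the size of the dilution. The matter should be corrected, but it does not threaten the primary analysis.

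**What to change.** - Check the actual wording of Q9-11. If the items have no suicide stem, rename the outcomes in 1.2, 1.3 and 2.5 as help-seeking behaviour for mental health problems and help-seeking intentions for personal or emotional problems. If they do have one, correct the descriptions in 3.1. In either case make hypotheses 3 and 4 use the same qualifiers as the objectives.
- State in 1.2 and 1.3 that the conclusion on help-seeking behaviour rests on the 3-month survey, and report the immediate-post AHSQ result as descriptive only.
- Leave the AHSQ recall wording unchanged. Asking about the time since the last survey would remove the overlap, but it would set a window of 3 to 6 weeks against a 3-month baseline window. Section 3.3 compares later occasions with baseline, so the shorter window would lower post-programme reporting mechanically.

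The cost is editorial, apart from giving up a confirmatory early result for one secondary outcome. No change to the survey is needed.

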## 2.6 Participant timeline

Among schools being evaluated, students will complete the same questionnaire on three different occasions:

1. Immediately pre-intervention (baseline)
2. immediately post-intervention
3. 3-month follow-up

## 2.7 Sample size

We estimate that 15 government schools and 18 Independent/Catholic schools will be eligible to participate. The specific numbers of schools, staff and students per site is as follows:

1. Government schools: 15 eligible schools and 2378 Year 9 students.
2. Non-government schools: 18 eligible schools and 2494 Year 9 students.

Given that school participation rates are estimated to range between 50-65% ( $19 \times 0.5 = 7.5$ ), and the proportion of students from participating schools returning consent forms will be approximately 20% ( $1189 / 0.2 = 238$ ), an initial sample size for the Cluster A & B schools is set at a conservative 119 students per Cluster.

## 3. Methods: Data collection, management, and analysis

---

### 3.1 Data collection methods

Data will be collected via a student questionnaire, which will be available as an online survey hosted on Qualtrics, or as a pen and paper survey, depending on individual school preference. Prior to administration, consenting students will be allocated a unique ID. For the online survey, this will be paired with a unique password that can only be used for its corresponding ID, to ensure that only students who have consent complete the survey.

A copy of the survey can be found in Appendix A. The scales included in the survey are listed below:

#### **Basic demographic information (Q1-8)**

Data will be collected on basic demographics – name of school, age, ATSI identity, language spoken at home, gender, who lives at home, and sexual orientation.

#### **Actual Help-Seeking Questionnaire (modified) (Q9-10)**

The AHSQ assesses recent actual help-seeking behaviour in which the respondent either does or does not report having sought help from for a mental health problem in the past 3 months. In addition to the AHSQ, actual help-seeking from adults is measured by four items (yes/no) that assess the experience of help-seeking from adults, conditional on responses to the AHSQ. If students indicate that they have sought help from at least one adult for a mental health problem on the AHSQ, then four questions will be presented asking whether any of the adults that they have had contact with have made them feel supported, helped them get

through the situation, made the situation worse, or made them more likely to seek further help from adults. These items were drawn from the previous US Sources of Strength trial

**General Help-Seeking Questionnaire (modified) (Q11)**

The GHSQ assesses intentions to seek help for personal or emotional problems from 11 different formal and informal sources (e.g. friend, parent, psychologist, or teacher). Respondents indicate how likely they are to seek help from each of the sources on a scale ranging from 1 (extremely unlikely) to 7 (extremely likely).

**Attitudes to seeking help from personnel at school (Q12-13)**

This is assessed by two measures, including the help-seeking from adults in general and adults at school. Both scales have four-items which were derived from the previous US Sources of Strength trial. These measures assess attitudes and perceived norms about seeking help from adults on a scale from 1 (strongly disagree) to 4 (strongly agree). On the help-seeking from adults, the items include ‘I know adults who could help a friend thinking of suicide’ and ‘My school has people who can help students going through hard times’. The items on the ‘adults at school’ scale enquire as to whether, if really upset and needing help, a student would talk to a counsellor or other adult at school, whether they believe these adults could help, and whether friends and family would want them to seek help. Items on this scale are summed, with higher scores reflecting more positive help-seeking from adults at school.

**Paykel’s Suicidal Feelings in the General Population Questionnaire (Q14)**

This questionnaire contains five questions assessing suicidal ideation and intent. Examples of the items include whether they felt life was worth living, whether they had wished they were dead, through to whether they have seriously considered taking their life. Each item is rated on a 5-point Likert scale indicating the frequency with which it may occur for the person. Two additional items have been added asking ‘Have you ever tried to take their own life?’, and if so, if this occurred in the past two weeks, the past year, or earlier.

**Self-harm (Q15-Q19)**

Self-harm is measured using three items (yes/no) that assess the presence of self-injury, whether the intention of the self-injury was to experience pain or suffering and whether the intention of the self-injury was to die. These items have been drawn from the evaluation of the Sources of Strength program.

**Stigma of Suicide Scale (SOSS) – Short Form (Q20)**

The SOSS contains a list of descriptors of people who attempt or die by suicide. The SOSS has three subscales: stigma, isolation/depression, and glorification/normalisation. The subscales and their corresponding descriptors are listed below:

Stigma	Isolation/depression	Glorification/normalisation
An embarrassment	Disconnected	Brave
Cowardly	Isolated	Dedicated
Immoral	Lonely	Noble
Irresponsible	Lost	Strong
Pathetic		
Shallow		
Stupid		
Vengeful		

Participants are asked the extent to which they agree with each descriptor on a scale of “1 - Strongly disagree”, “2 - Disagree”, “3 - Neither agree nor disagree”, “4 - Agree”, and “5 - Strongly Agree”. Higher scores on this scale are suggestive of greater suicide stigma.

Definitions have been provided for ‘Noble’ (‘honourable or having good character’) and ‘Vengeful’ (‘wanting to get revenge’), based on feedback from SERAP that these terms may be confusing to Year 9 students.

